5.4.3.1. Rules For Dose Delay/Interruption/Discontinuation

Events including, but not limited to, pneumonitis, colitis, creatinine, and liver function test (LFT) elevation should be monitored carefully with this class of agents. To facilitate the early recognition and prompt intervention in the event of clinically AEs related to study treatment, management algorithms have been developed for suspected pulmonary, gastrointestinal, liver, endocrine, skin, cardiac, renal, or other immune-related toxicities (See [Appendix 8](#)). For non-irAEs, please refer to the rules for dose delay/interruption/discontinuation below:

- Withhold treatment for: creatinine, AST, ALT, or total bilirubin for drug-related Grade 2 elevations except if they were >ULN at baseline.
- Withhold treatment for any other Grade 3 drug-related AEs.
- Resume treatment when drug-related AE recovers to Grade 0-1 except when creatinine, AST, ALT, or total bilirubin were >ULN at baseline.
- Discontinue treatment for drug-related Grade 3-4 creatinine, AST, ALT, or total bilirubin elevations except if they were >ULN at baseline.
- Discontinue treatment for any other Grade 4 drug-related AEs or laboratory abnormality, except for the following events which do not require discontinuation:
 - Isolated Grade 4 amylase or lipase abnormalities that are not associated with symptoms or clinical manifestations of pancreatitis and decrease to <Grade 4 within 1 week of onset.
 - Isolated Grade 4 electrolyte imbalances/abnormalities that are not associated with clinical sequelae and are corrected with supplementation/appropriate management within 72 hours of their onset.
- Discontinue treatment for persistent Grade 2-3 drug-related AE that do not recover to Grade 0-1 within 12 weeks after last dose except when creatinine, AST, ALT, or total bilirubin were >ULN at baseline.
- Discontinue treatment for any Grade 3-4 drug-related AE that recurs.
- If creatinine >ULN at baseline, withhold treatment for drug-related elevation >1.5 x baseline and resume when ≤ 1.5 x baseline. Discontinue treatment with drug-related elevation >3 x baseline or drug-related elevation that does not recover to ≤ 1.5 x baseline within 12 weeks after last dose.

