
Grade 3 to 4 Grade 3: Covering $>$30% body surface area; Grade 4: Life threatening consequences
	
 -Withhold study treatment for Grade 3. -Permanently discontinue for Grade 4 or recurrent Grade 3. -Consider skin biopsy. -Dermatology consult. -1.0 to 2.0 mg/kg/day prednisone or equivalent. -Add prophylactic antibiotics for opportunistic infections. 	
 -If improves to Grade \leq1: -Taper steroids over at least 1 month; resume study treatment following steroids taper (for initial Grade 3).

Pulmonary irAEs		
Grade of Pneumonitis (NCI-CTCAE v4)	Initial Management	Follow-up Management
Grade 1 Radiographic changes only	-Consider withholding study treatment. -Monitor for symptoms every 2 to 3 days. -Consider Pulmonary and Infectious Disease consults.	-Re-assess at least every 3 weeks. -If worsens: Treat as Grade 2 or Grade 3 to 4.
Grade 2 Mild to moderate new symptoms	-Withhold study treatment. -Pulmonary and Infectious Disease consults. -Monitor symptoms daily; consider hospitalization. -1.0 to 2.0 mg/kg/day prednisone or equivalent. -Add prophylactic antibiotics for opportunistic infections. -Consider bronchoscopy, lung biopsy.	-Re-assess every 1 to 3 days If improves: -When symptoms return to Grade ≤ 1 , taper steroids over at least 1 month, and then resume study treatment following steroids taper. -If not improving after 2 weeks or worsening: Treat as Grade 3 to 4.
Grade 3 to 4 Grade 3: Severe new symptoms; New/worsening hypoxia; Grade 4: Life-threatening	-Permanently discontinue study treatment. -Hospitalize. -Pulmonary and Infectious Disease consults. -1.0 to 2.0 mg/kg/day prednisone or equivalent. -Add prophylactic antibiotics for opportunistic infections. -Consider bronchoscopy, lung biopsy.	-If improves to Grade ≤ 1 : -Taper steroids over at least 1 month. -If not improving after 48 hours or worsening: Add additional immunosuppression (for example, infliximab, cyclophosphamide, IV immunoglobulin, or mycophenolate mofetil).

Hepatic irAEs		
Grade of Liver Test Elevation (NCI-CTCAE v4)	Initial Management	Follow-up Management
Grade 1 Grade 1 AST or ALT > ULN to 3.0 x ULN and/or Total bilirubin > ULN to 1.5 x ULN	-Continue study treatment.	-Continue liver function monitoring. -If worsens: Treat as Grade 2 or 3 - 4.

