Grade 2 AST or ALT >3.0 to ≤5 x ULN and/or total bilirubin >1.5 to ≤3 x ULN	-Withhold study treatment. -Increase frequency of monitoring to every 3 days.	-If returns to Grade ≤1: -Resume routine monitoring; resume study treatment. -If elevation persists > 5 to 7 days or worsens: -Treat as Grade 3 to 4.
Grade 3 to 4 AST or ALT >5 x ULN and/or total bilirubin >3 x ULN	-Permanently discontinue study treatment. -Increase frequency of monitoring to every 1 to 2 days. -1.0 to 2.0 mg/kg/day prednisone or equivalent. -Add prophylactic antibiotics for opportunistic infections. -Consult gastroenterologist/hepatologist. -Consider obtaining MRI/CT scan of liver and liver biopsy if clinically warranted.	-If returns to Grade ≤1: -Taper steroids over at least 1 month. -If does not improve in >3 to 5 days, worsens or rebounds: -Add mycophenolate mofetil 1 gram (g) twice daily. -If no response within an additional 3 to 5 days, consider other immunosuppressants per local guidelines.

Renal irAEs		
Grade of Creatinine Increased (NCI-CTCAE v4)	Initial Management	Follow-up Management
Grade 1 Creatinine increased > ULN to 1.5 x ULN	-Continue study treatment.	-Continue renal function monitoring. -If worsens: Treat as Grade 2 to 3 or 4.
Grade 2 to 3 Creatinine increased >1.5 and ≤6 x ULN	-Withhold study treatment. -Increase frequency of monitoring to every 3 days. -1.0 to 2.0 mg/kg/day prednisone or equivalent. -Add prophylactic antibiotics for opportunistic infections. -Consider renal biopsy.	-If returns to Grade ≤1: -Taper steroids over at least 1 month, and resume study treatment following steroids taper. -If worsens: -Treat as Grade 4.
Grade 4 Creatinine increased >6 x ULN	-Permanently discontinue study treatment. -Monitor creatinine daily. -1.0 to 2.0 mg/kg/day prednisone or equivalent. -Add prophylactic antibiotics for opportunistic infections Consider renal biopsy. -Nephrology consult.	-If returns to Grade ≤1: Taper steroids over at least 1 month.

Cardiac irAEs		
Myocarditis	Initial Management	Follow-up Management

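### Appendix 8 ties renal and hepatic irAE recovery to Grade ≤1 with no baseline alternative, so a patient who was eligible above 1.5 x ULN and is back at the entry value does not meet the printed taper or resume condition (minor wording correction)

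*Protocol*

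**What the plan says.** **Grade 1 ceilings (Protocol Appendix 8).** The renal table gives Grade 1 as "Creatinine increased > ULN to 1.5 x ULN". The hepatic table gives "Total bilirubin > ULN to 1.5 x ULN", and 3.0 x ULN for AST and ALT.

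**Recovery conditions.** Four rows depend on a return to Grade ≤1:

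- Renal Grade 2 to 3 (creatinine >1.5 to 6 x ULN): drug withheld and steroids given; on recovery, "Taper steroids over at least 1 month, and resume study treatment following steroids taper".
- Renal Grade 4: drug stopped permanently; recovery governs the taper only.
- Hepatic Grade 2, "AST or ALT >3.0 to ≤5 x ULN and/or total bilirubin >1.5 to ≤3 x ULN": drug withheld, no steroids; recovery allows resumption. "If elevation persists > 5 to 7 days or worsens", the patient is handled as Grade 3 to 4.
- Hepatic Grade 3 to 4: drug stopped permanently and steroids given; "If returns to Grade ≤1: -Taper steroids over at least 1 month".

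**Eligibility (4.1.1 and 4.1.2).** Creatinine must be ≤1.5 x ULN or, alternatively, clearance must be ≥40 mL/min (Part 1) or ≥30 mL/min (Part 2). Bilirubin must be ≤1.5 x ULN, but <3 x ULN in Gilbert syndrome. AST and ALT must be ≤3.0 x ULN.

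**The parallel rule (5.4.3.1).** "Resume treatment when drug-related AE recovers to Grade 0-1 except when creatinine, AST, ALT, or total bilirubin were >ULN at baseline". For those patients it sets resume limits as multiples of baseline. The list is introduced with "For non-irAEs, please refer to the rules for dose delay/interruption/discontinuation below"; irAEs are sent to Appendix 8.

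**The concern.** The entry criteria knowingly admit some patients whose normal state lies above the Appendix 8 Grade 1 ceiling. If such a patient later has a renal or hepatic event judged immune-related and recovers completely, the printed recovery condition is still unmet.

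Taken literally, the renal Grade 2 to 3 patient then has no printed trigger to taper prednisone at 1.0 to 2.0 mg/kg/day or to restart study drug. The hepatic Grade 2 patient cannot resume, and after 5 to 7 days may be moved to the row for permanent discontinuation and steroids. The protocol solves the same problem for non-irAEs, so this looks like an omission. Baseline-relative wording also fits the appendix, which grades diarrhea by stools above baseline.

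**Working it through.** The plan states no figure to reproduce. The check compares entry limits with recovery limits.

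**1. Who can be at baseline and fail the condition?**

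| Analyte | Highest entry value | Grade 1 ceiling | Gap? |
|---|---|---|---|
| Creatinine | above 1.5 x ULN if clearance is sufficient | 1.5 x ULN | Yes |
| Bilirubin, Gilbert | <3 x ULN | 1.5 x ULN | Yes |
| Bilirubin, others | 1.5 x ULN | 1.5 x ULN | No |
| AST/ALT | 3.0 x ULN | 3.0 x ULN | No |

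**2. How far below baseline must the value fall?** For a baseline of b x ULN the required fall is 1 − 1.5/b.

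- b = 1.6: 6.2%
- b = 1.8: 16.7%
- b = 2.0: 25.0%

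**3. Can a Part 1 patient enter above 1.5 x ULN?** Criterion 8 of 4.1.1 prints the Cockcroft-Gault formula. Solved for a man at the limit of 40 mL/min, creatinine = (140 − age) x weight / (72 x 40). At 60 years and 80 kg this is 80 x 80 / 2880 = 2.22 mg/dL. The documents give no creatinine ULN, so I assume 1.1 to 1.3 mg/dL.

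| Assumed ULN (mg/dL) | Baseline (x ULN) | Fall needed | Fold rise that stays ≤6 x ULN |
|---|---|---|---|
| 1.1 | 2.02 | 25.8% | 2.97 |
| 1.2 | 1.85 | 19.0% | 3.24 |
| 1.3 | 1.71 | 12.2% | 3.51 |

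He is eligible, and a roughly three-fold rise still leaves him in the row that allows resumption.

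The route is limited. To enter above 1.5 x ULN, a 70-year-old man must weigh more than 1.5 x ULN x 2880 / 70, which is 67.9, 74.1 or 80.2 kg at the three assumed ULNs. Part 2 uses CKD-EPI, whose equation is not in the documents, so I have not computed it.

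**4. How does a Gilbert patient reach the hepatic Grade 2 row?** One way is a bilirubin rise that stays at or below 3 x ULN. The room for that is 3 − b: 1.4, 1.2, 1.0, 0.5 and 0.1 x ULN at b = 1.6, 1.8, 2.0, 2.5 and 2.9. The other is a Grade 2 AST/ALT event with bilirubin unchanged, because the row joins the two analytes with and/or. At high Gilbert baselines the second route is almost the only one. Above 3 x ULN bilirubin the drug is stopped permanently for everyone, so only the taper is affected.

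**5. What would the non-irAE rule do?** Section 5.4.3.1 resumes at ≤1.5 x baseline for creatinine and ≤2 x baseline for bilirubin.

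- Creatinine baseline 1.8 x ULN: 1.5 x 1.8 = 2.7 x ULN, against 1.5 x ULN in Appendix 8.
- Bilirubin baseline 2.5 x ULN: 2 x 2.5 = 5.0 x ULN, against 1.5 x ULN.

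**The case against.** The strongest reply is that nobody would apply the table this way. Section 5.4.3 calls its dose modifications recommended, and 5.4.3.5 describes Appendix 8 as algorithms. Section 5.4.5 leaves adequate recovery to the investigator and requires sponsor agreement to resume after 4 weeks of interruption; with a taper of at least a month, most renal cases would reach that review. Section 5.7.6 leaves immunosuppression for irAEs to local practice. AEs are recorded as new or worsening conditions since baseline, so an unchanged Gilbert bilirubin can be read as no part of an ALT event.

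Much of this stands. A mechanical lock-out is unlikely, and the steroid limb is partly covered. But 5.7.6 does not govern resumption of study drug, 5.4.5 does not waive the Grade ≤1 condition, and recording AEs against baseline settles when an event starts, not when it has ended.

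A second objection concerns the remedy. Counting any elevation above baseline as persistent in the hepatic Grade 2 row would harm ordinary patients. Someone whose ALT goes from 0.8 x ULN at baseline to 4 at the event and 2 by day 4 resumes under the printed rule. Under that change, if still above 0.8 at day 8, the same patient would also qualify for permanent discontinuation. This objection is right, and the fix below avoids it. It is also fair that a patient resumed at 1.8 x ULN creatinine still sits in the band that says to withhold, so a clarifying note is needed.

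**Conclusion.** The gap is real and minor. In four Appendix 8 rows, a patient eligible above 1.5 x ULN for creatinine or bilirubin who is back at baseline does not meet the printed recovery condition. Resumption is affected in renal Grade 2 to 3 and hepatic Grade 2; in renal Grade 4 and hepatic Grade 3 to 4 only the taper is.

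A reader might infer more than this, and the documents do not support it:

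- That such patients will in practice be kept on steroids or discontinued. The latitude in 5.4.5 and 5.7.6 makes that unlikely, and no frequency is available.
- That everyone with an abnormal baseline is affected. Patients at or below 1.5 x ULN at entry, and all AST/ALT values, are not.
- That trial results are at risk. No endpoint or estimate uses these conditions. The DLT definition in 3.1.5 cites Appendix 8 for supportive care but counts grade and duration, not whether a taper or resume condition was met.

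The threshold comparison needs no assumption. The creatinine illustration rests on assumed ULNs of 1.1 to 1.3 mg/dL and on Part 1 only. The size of the subgroup is unknown.

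**What to change.** - **Four recovery conditions** (renal Grade 2 to 3, renal Grade 4, hepatic Grade 2, hepatic Grade 3 to 4): write *returns to Grade ≤1, or to baseline for creatinine or bilirubin that was above 1.5 x ULN at baseline*. Apply it per analyte, so AST and ALT must still reach Grade ≤1.
- **Hepatic Grade 2 persistence rule:** keep the trigger as it is and add only *a bilirubin at or below a baseline value that was above 1.5 x ULN does not count as a persisting elevation*.
- **One note:** a creatinine or bilirubin at such a baseline does not by itself re-trigger withholding.

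Leave all other thresholds and eligibility unchanged, and do not import the baseline multiples from 5.4.3.1.

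The cost is one phrase in four table cells, one added sentence and one note, with no new procedures or data. The downside is slightly more re-treatment after a renal or hepatic irAE in this small subgroup.

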Appendix 9. Subcutaneous Injection Site Location Diagram

Injection site locations include a maximum of 8 unique administration sites distributed across 4 abdominal quadrants with a possibility of up to 2 injection locations per quadrant. Location 1 is proximal to the umbilicus and Location 2 is distal to the umbilicus.

Administer the required number of injections in the following order:

1. Lower Left Quadrant Location 1
2. Lower Right Quadrant Location 1
3. Lower Left Quadrant Location 2
4. Lower Right Quadrant Location 2
5. Upper Right Quadrant Location 1
6. Upper Left Quadrant Location 1
7. Upper Right Quadrant Location 2
8. Upper Left Quadrant Location 2

Injections to the abdomen are preferred. If SC injections in the abdominal location are not possible, SC injections can be administered in a distributed manner in the thighs. SC injections in the upper extremities (eg, deltoid, upper and lower arm) are not permitted.

Track the patient's injection site(s) sequentially on this diagram with a red pen and mark the injection sites on the patient's abdomen according to your clinic's standard practice.

Record the location, time of each injection and any injection site reactions in the patient's source records and study CRF. Complete one CRF per injection.

1. VERSION HISTORY

Amendment 2	Section	Update
	5.5	A new section is added to address the analysis strategies on data that is impacted by the COVID-19 pandemic.
	Appendix 9.2	Removed the PFS window. The statistical programming standard for this study is switching from Pfizer Data Standard (PDS) to CaPS (CDISC and Pfizer Standard), to be consistent with the late stage studies of the program (B8011006 and B8011007) that are being conducted at the time of this SAP amendment. In CaPS, the PFS window is no longer required. Table 9.2.1 and 9.2.2 are updated to be consistent with CaPS requirements.
Amendment 1	Section	Update
	All	Texts taken directly from the protocol are made italicized
	2.1	Objectives are updated and reformatted per protocol amendment 3
	2.2	Study design is updated per protocol amendment 3
	3	Endpoints are updated per protocol amendment 3
	4	Analysis sets are updated per protocol amendment 3
	5.2.2.	Statistical decision rules are updated for Part 2 per protocol amendment 3
	5.3	General statistical methods are updated with additional details for programming personnel
	6	Details about unconfirmed and confirmed tumor response and progression for RECIST 1.1 and irRECIST added.
	6.1	Cycle delay is updated; Cycle skip is added
	6.3.1	Editorial changes were made to the efficacy endpoints analyses
	7	Informal data monitoring is added
	9.6	All lymphoma response assessment is removed per protocol amendment 3

2. INTRODUCTION

This SAP provides the detailed methodology for summary and statistical analyses of the data collected in study B8011001. This document may modify the plans outlined in the protocol; however, any major modifications of the primary endpoint definition or its analysis will also be reflected in a protocol amendment. This SAP amendment is based on the protocol amendment 3 dated June 3, 2017.

Note: in this document any text taken directly from the protocol is *italicized*.

2.1. Study Objectives

Part 1 (Dose-Escalation) Primary Objective

- To assess safety and tolerability of increasing dose levels of PF-06801591 in patients with locally advanced or metastatic melanoma, SCCHN, ovarian carcinoma, sarcoma, NSCLC, urothelial carcinoma or other solid tumor types with clinical evidence of response to anti PD-1 or PD-L1 agents to establish the MTD.
- To assess safety and tolerability of PF-06801591 administered SC in patients with locally advanced or metastatic melanoma, SCCHN, ovarian cancer, sarcoma, NSCLC, urothelial carcinoma or other solid tumor types with clinical evidence of response to anti PD-1 or PD-L1 agents.

Part 1 (Dose-Escalation) Secondary Objective

- To characterize the single-dose and multiple-dose PK of PF-06801591 following IV or SC administration.
- To evaluate the immunogenicity of PF-06801591 following repeated administration.
- To characterize PD-1 receptor occupancy (RO) in peripheral blood T cells following IV or SC PF-06801591 administration at each dose level.
- To evaluate preliminary anti-tumor activity of PF-06801591.

CCI

CCI

Part 2 (Dose-Expansion) Primary Objective

- *To further characterize the safety and tolerability of PF-06801591 following SC administration in NSCLC and urothelial carcinoma.*
- *To estimate clinical efficacy by overall response rate (ORR) of PF-06801591 following SC administration in NSCLC and urothelial carcinoma.*

Part 2 (Dose-Expansion) Secondary Objective

- To further evaluate preliminary anti-tumor activity of PF-06801591 following SC administration.
- *To evaluate overall survival (OS).*
- To collect PF-06801591 drug concentration data in patients following SC administration for evaluation of population PK.
- To evaluate the immunogenicity of PF-06801591 following repeated SC administration.

CCI

[figure not shown]

CCI

2.2. Study Design

This is a Phase 1, open-label, multi-center, multiple-dose, dose escalation and expansion, safety, PK, and PD study of PF-06801591 in previously treated patients with locally advanced or metastatic solid tumor types with clinical evidence of response to anti PD-1 or PD-L1 agents. This clinical trial will include 2 parts: Part 1 dose escalation and Part 2 dose expansion (Figure 1). A total of approximately 140 patients will be enrolled into this study.

Figure 1 B8011001 Study Schematic

Part 1 will enroll patients with locally advanced or metastatic melanoma, SCCHN, ovarian cancer, sarcoma, NSCLC, urothelial carcinoma, or other solid tumor types with clinical evidence of response to anti PD-1 or PD-L1 agents. Patients will receive 0.5, 1, 3, or 10 mg/kg PF-06801591 intravenously (IV) every 3 weeks (q3w), or 300 mg PF-06801591 subcutaneously every 4 weeks (q4w). The Part 1 dose escalation phase will enroll approximately 8 to 15 patients per dose level.

Part 1 will be further divided into Part 1A (safety cohort) CCI [REDACTED]. For both IV and SC administration portions, each safety cohort will enroll 2-4 patients per dose level. CCI [REDACTED]

All patients in Part 2 will receive 300 mg PF-06801591 SC q4w. Part 2 dose expansion will include 2 arms: Arm 1 will enroll approximately 60 patients with NSCLC who progressed on or were intolerant to systemic therapy or for whom systemic therapy was refused or unavailable but have not previously received anti-PD-1 or anti-PD-L1. Arm 2 will enroll approximately 40 patients with urothelial carcinoma who progressed on or were intolerant to systemic therapy or for whom systemic therapy was refused or unavailable but have not previously received anti-PD-1 or anti-PD-L1. Approximately 100 patients will be enrolled into Part 2.

2.2.1. MTD Determination (Part 1)

Part 1 will study sequential cohorts (0.5, 1, 3, and 10 mg/kg, or 300 mg SC) of PF-06801591 in adult patients with locally advanced or metastatic melanoma, SCCHN, ovarian cancer, sarcoma, NSCLC, urothelial carcinoma, or other solid tumor types with clinical evidence of response to anti-PD-1 or PD-L1 agents who are unresponsive to currently available therapies or for whom no standard therapy is available. An mTPI method, targeting a dose limiting toxicity (DLT) rate of 27.5% will be utilized for dose escalation. In the IV administration portion, if based on Part 1A information the dose level is deemed safe and well-tolerated, an additional 2 to 5 patients will enroll into the same dose level in Part 1B. In the SC administration portion, if based on Part 1A information the 300 mg dose level is deemed safe and well-tolerated, up to an additional 11 patients (approximately) will be enrolled into Part 1B. Up to approximately 9 patients may be enrolled into each dose level in the IV administration portion, and up to approximately 15 patients may be enrolled into the 300 mg SC administration cohort (Part 1A and Part 1B combined). The mTPI approach would be applied across Parts 1A and 1B to ensure that administered doses do not surpass the toxicity boundaries. Safety data from all patients in Parts 1A (safety cohort) CCI [REDACTED] will be used to determine the MTD. The dose finding decision will be based on 1-cycle (21-day) DLT observation for patients enrolled into IV administration portion and 1-cycle (28-day) DLT observation for patients enrolled into subcutaneous dosing portion. A staggered start will be employed at all dose levels. A single patient will be dosed and observed for 48 hours. If no safety concerns arise during this 48-hour period, a second patient will be enrolled into the same dose level cohort.

Late immune-related DLTs are irAEs that meet the same grading criteria as DLT criteria but occur after the initial 21-day DLT period for IV administration, or 28 days for SC administration, and during the 120-day assessment period. Late immune-related DLTs will be added to the mTPI approach to reassess the dose-finding decisions.

Safety information, provided by additional patients enrolled into each dose level expansion will also be taken into account for MTD determination. If the DLT rate is estimated to reach >33% or more at any dose level, enrollment at that level and all higher levels will be temporarily stopped, and safety data will be analyzed. The decision to move forward with enrollment will follow the

same DLT target as described previously. Dose escalation will continue until an MTD has been established or a prespecified maximum dose level has been reached.

The mTPI method relies upon a statistical probability algorithm, calculated using all patients treated in the current dose level to determine one of the following dose-finding decisions: the subsequent dose should be escalated, maintained at the current dose, or de-escalated in the next cohort of 2 to 4 patients, or the trial should be terminated (see Table 1).

In principle, all patients must be evaluated for a minimum period of 21 days (q3w dosing interval) or 28 days for the subcutaneous cohort. If a patient withdraws from the study before Day 21 (or 28 days for the subcutaneous cohort) for reasons other than drug-related toxicity, another patient may be enrolled to replace that patient in the current cohort. However, if a patient discontinues close to Day 21 (or 28 days for the subcutaneous cohort) for reasons other than toxicity and due to an evident nondrug-related event, the patient may be deemed evaluable for safety if safety assessments have been unremarkable and the investigator and sponsor’s medical monitor both agree that the patient is evaluable for DLT safety observation.

Table 1. Decision Rules

Number of Patients having DLT	Number of Patients Treated at a Dose Level													
	n=2	n=3	n=4	n=5	n=6	n=7	n=8	n=9	n=10	n=11	n=12	n=13	n=14	n=15
0	E	E	E	E	E	E	E	E	E	E	E	E	E	E
1	S	S	S	E	E	E	E	E	E	E	E	E	E	E
2	U	D	S	S	S	S	S	S	S	E	E	E	E	E
3		U	U	D	D	S	S	S	S	S	S	S	S	S
4			U	U	U	U	D	D	D	S	S	S	S	S
5				U	U	U	U	U	D	D	D	D	D	S
6					U	U	U	U	U	U	U	D	D	D
7						U	U	U	U	U	U	U	U	U

Actions to be taken:

D = De-escalate the dose; E: Escalate the dose; S: Stay at the dose.

U = Unacceptable toxicity.

The dose escalation Part 1 of the study will stop if any of the following criteria is met:

1. The maximum sample size has been achieved (approximately 40 patients in total);
2. 6 to 15 patients have been enrolled at a dose level that is predicted to be the MTD per the mTPI method;
3. All dose levels explored appear to be overly toxic, and the MTD cannot be determined;
4. All candidate dose levels have been tested and deemed safe.

